### 6.3.2 Secondary Efficacy Variables

#### *Secondary Endpoints*

All endpoints achieved within 30 day period after end of study drug treatment:

- Number and percentage of subjects with complete remission (defined as confirmed platelet response and absence of exacerbation)
- Number and percentage of (subjects with) exacerbations of TTP (defined as recurrent thrombocytopenia following a confirmed platelet response and requiring a re-initiation of daily PE treatment after  $\geq 1$  day but  $\leq 30$  days after the last daily PE) and time to first exacerbation of TTP
- Number of daily PE sessions, number of total volume of plasma administered and number of days of daily PE
- Total mortality within the PE treatment period and within the subsequent study drug treatment period (including tapering)
- Number and percentage of subjects relapsing of TTP (defined as *de novo* event of TTP that occurs later than 30 days after the last daily PE)
- Number and percentage of subjects with platelets  $\geq 150,000/\mu$ L at day 30 of study drug administration (last treatment day visit) and one month follow-up time point
- Resolution or improvement (improvement of  $\geq 1$  grade in the CTCAE v4.0 scale) of TTP-related signs and symptoms as captured on physical examination and as adverse events, at complete remission and at end of the study drug treatment period (including tapering) (by number of unique subjects and by total number of AEs)
- Incidence of PE treatment-related AEs, such as, but not restricted to: haemorrhage from catheter insertion, sepsis, catheter thrombosis, pneumothorax, fluid overload, hypoxia, hypotension, anaphylactoid reactions and TRALI

---

This study has been statistically powered for the primary endpoint. No adjustment for multiplicity has been applied to the exploratory analysis for the secondary variables. All analysis will be performed on the ITT and PP populations and any p-values presented for secondary efficacy variables are purely exploratory (e.g. comparison of the number and percent of subjects with complete remission, exacerbations, relapse and daily PEs).

The number and percentage of subjects with complete remission at one month post first administration of study treatment, along with the exact binomial CI of the percentage will be presented by treatment group, overall and by ADAMTS13 activity  $< 5\%$  vs.  $\geq 5\%$  at baseline.

The number and percentage of (subjects with) exacerbations of TTP at one month post first administration of study treatment, along with the exact binomial CI of the percentage will be presented by treatment group, overall and by ADAMTS13 activity  $< 5\%$  vs.  $\geq 5\%$  both at baseline and after last PE (measured on day 1 after last daily PE). The time to first exacerbation of TTP, from first study drug administration, will follow the same analysis method as the primary efficacy endpoint and will be presented graphically.

The number and percentage of subjects relapsing of TTP at one month post first administration of study treatment, along with the exact binomial CI of the percentage will be presented by treatment group, overall and by ADAMTS13 activity  $< 5\%$  vs.  $\geq 5\%$  both at baseline and after last PE (measured on day 1 after last daily PE). The time to first relapse of TTP, from first study drug administration, will be presented graphically.

The number and percentage of subjects with exacerbation and/or relapse, along with the exact binomial CI of the percentage will be presented by treatment group, overall and by ADAMTS13 activity  $< 5\%$  vs.  $\geq 5\%$  both at baseline and after last PE (measured on day 1 after last daily PE). The time to first exacerbation or relapse (whichever occurs first), for first study drug administration, will be presented graphically.

The number of daily PE sessions (all PE sessions during the daily PE period, which may include more than one PE per day), total volume of plasma administered, number of days

---

of PE (number of days with at least one PE administration) and number of consecutive days of PE (maximum number of days per subject where there was no interruption of PE) will be summarised descriptively by treatment group, overall, by ADAMTS13 activity < 5% vs.  $\geq$  5% at baseline and by having received first PE before randomisation or not.

The number and percentage of unique subjects with resolved or improved TTP-related signs and symptoms as captured on physical examination and as adverse events within the PE treatment period, within the ensuing 30 days and at the one month follow-up will be summarised by treatment and overall along with the exact binomial CI of the percentage. Improvement of physical examination is defined as progressing from an abnormal to a normal result for a particular system at a given time point. Resolution of physical examination is defined as having normal results for all systems at a given time point. Resolution of an adverse event is defined as having a stop date present and an outcome of either 'resolved' or 'resolved with sequelae' within the given period. Both physical examination systems and adverse events flagged as being related to TTP will be considered.

The number and percentage of deaths within the PE treatment period, within the ensuing 30 days (study treatment period) and within the period from the end of the study treatment period up to and including the one month follow-up will be presented for each treatment group and overall for the ITT population only. Each death will be categorised into one of the distinct periods identified above, such that the death is counted only once in the table.

The incidence of PE treatment-related AEs, such as, but not restricted to: hemorrhage from catheter insertion, sepsis, catheter thrombosis, pneumothorax, fluid overload, hypoxia, hypotension, anaphylactoid reactions and transfusion related acute lung injury (TRALI) will be summarised by system organ class, preferred term, treatment group and overall. The summary will be repeated for PE treatment-related SAEs for the ITT population only.

---

Frequency tables (with accompanying Chi-square p-values) will be made for the following characteristics: use of corticosteroids during daily PE, use of rituximab during daily PE and tapering. Use of corticosteroids will be determined by using the Concomitant Medications data (both PE related and not PE related) with ATC codes beginning with “H02” (systemic corticosteroids). Use of rituximab will be determined by using the Concomitant Medications data (both PE related and not PE related) with ATC code “L01XC” (coded term “RITUXIMAB”).

The number and percentage of subjects with platelets  $\geq 150,000/\mu\text{L}$  (regardless of confirmation) at Day 30 of study drug administration (i.e. the last administration of study drug) and at the one month follow-up will be summarised by treatment and overall along with the exact binomial CI of the percentage.

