4.1.2 Secondary Endpoints

All endpoints achieved within 30 day period after end of study drug treatment:

- Number of subjects with complete remission (defined as confirmed platelet response and absence of exacerbation)
- Number of (subjects with) exacerbations of TTP (defined as recurrent thrombocytopenia following a confirmed platelet response and requiring a re-initiation of daily PE treatment after ≥ 1 day but ≤ 30 days after the last daily PE) and time to first exacerbation of TTP
- Number of subjects relapsing of TTP (defined as *de novo* event of TTP that occurs later than 30 days after the last daily PE)
- Number of daily PE sessions, number of plasma units administered and number of days of daily PE
- Resolution of non-focal neurological symptoms as defined by neurocognitive function at complete remission, measured by a neurocognitive test battery
- Resolution or improvement (improvement of ≥ 1 grade in the CTCAE v4.0 scale) of TTP-related signs and symptoms as captured on physical examination and as adverse events, at complete remission and at end of the study drug treatment period (including tapering) (by number of unique subjects and by total number of AEs)
- Total mortality within the PE treatment period and within the subsequent study drug treatment period (including tapering)
- Incidence of PE treatment-related AEs, such as, but not restricted to: haemorrhage from catheter insertion, sepsis, catheter thrombosis, pneumothorax, fluid overload, hypoxia, hypotension, anaphylactoid reactions and TRALI

- Incidence and severity of ALX-0081 treatment-emergent AEs and relationship to study drug
- Development of ADA \leq 30 days post-last study drug treatment
- PK and PD profile

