4.3 Overview of Treatment and Dosing Regimen for Study Drug

The primary treatment for acquired TTP is daily PE. Immunosuppressive treatment is also often administered. The centres will follow their respective guidelines for the treatment of TTP patients, regarding all items other than the study drug. Discontinuation of daily PE depends on normalisation of platelet count, neurological status and other clinical and laboratory parameters. The frequency of PE is occasionally reduced ('tapered') rather than stopping completely at time of response, however this is not based on randomised clinical trial data and is not recommended per this protocol (although it is allowed if considered necessary by the Investigator).

The study drug will be administered as adjunctive treatment at specific times relative to the PE procedures.

The first administration is a single i.v. bolus injection, administered by a push injection. All subsequent administrations are s.c. injections. The study drug consists of 10 mg of ALX-0081 or placebo, once daily (except if PE is given twice daily, then study drug is 10 mg twice daily) as described in Section 7.2.

Note that, in case of re-initiation of daily plasma exchange due to exacerbation, no i.v. bolus injection will be administered prior to the first new PE session; daily s.c. study drug administration will continue per protocol.

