Complete remission: Complete remission is defined as recovery of platelets (confirmed by platelets  $\geq 150,000/\mu\text{L}$  and LDH  $\leq 2 \times \text{ULN}$  at 48 hrs after initial platelet response) and absence of exacerbation.

Initial platelet recovery: Date of initial platelet recovery is defined as the first occurrence of platelets  $\geq 150,000/\mu\text{L}$  which is **confirmed** 48 hours later by platelets  $\geq 150,000/\mu\text{L}$  and LDH  $\leq 2 \times \text{ULN}$ . For example, if platelets reach  $\geq 150,000/\mu\text{L}$  on Day 5, are not confirmed at Day 7, reach  $\geq 150,000/\mu\text{L}$  again on Day 10 and are confirmed at Day 12, the initial platelet recovery occurs on Day 10. Initial platelet recovery and confirmation dates will be determined using the actual lab results, following standardisation to consistent units.

Time to Response: Time to response will be calculated as the number of days, hours and minutes (represented by number of days with two significant digits after the decimal point) from study drug administration to initial platelet recovery, as defined above. An

---

observation is censored if the observation does not meet the defined time interval of 30 days, due to any cause of loss-to follow-up (including death), or endpoint not being reached.

Subjects that attain confirmed platelet response:

Time-to-Response = [Date and time (hrs, min) of initial platelet recovery] – [Date and time (hrs, min) of first study drug administration]

Exacerbation: Exacerbation of TTP is defined as recurrent thrombocytopenia following a confirmed platelet response and requiring a re-initiation of daily PE treatment  $\geq 1$  day but  $\leq 30$  days after the last daily PE.

Relapse: Defined as de novo event of TTP that occurs later than 30 days after the last daily PE.

First PE: Defined as start of PE.

First on-study PE: Defined as first PE received after randomisation.

In case first on-study PE is not first PE, then first on-study PE should be started within 24 hours (after the end) of the first PE. If not it is considered major protocol deviation.

Overall duration of study treatment exposure (days): Defined as date of last dose of study treatment – date of first dose of study treatment + 1

Duration of study treatment exposure during daily PE (days): Defined as date of last dose of study treatment during the daily PE period – date of first dose of study treatment during the daily PE period + 1

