#### 4. EFFICACY PARAMETERS

##### Clinical Outcomes:

- Time-to-response of treatment, defined by a recovery of platelets  $\geq 150,000/\mu\text{L}$ . This response must be confirmed at 48 hours after the initial reporting of platelet recovery above  $150,000/\mu\text{L}$  by a *de novo* measure of platelets  $\geq 150,000/\mu\text{L}$  and  $\text{LDH} \leq 2 \times \text{ULN}$
- Number and percentage of subjects with confirmed platelet response
- Number and percentage of subjects with complete remission
- Number and percentage of (subjects with) exacerbations of TTP and time to first exacerbation of TTP
- Daily PE data (total volume of plasma units administered and number of days of PE), including serious adverse events (SAEs) related to PE treatment
- Total mortality within the daily PE treatment period and within the subsequent study drug treatment period (including tapering). Note that tapering of PE is considered to be part of the subsequent study drug period rather than as part of the daily PE period.
- Number and percentage of subjects relapsing of TTP for a maximum of 1 year and time to first relapse of TTP
- Number and percentage of subjects with platelets  $\geq 150,000/\mu\text{L}$  at day 30 of study drug administration (last treatment day visit) and at 1 month follow-up time point
- Neurocognitive function (adults only), as measured by a neurocognitive test battery, at complete remission and at 1 year follow-up. Remission is defined as the absence of need for PE treatment  $\geq 30$  days. In adults, this test will be preceded by the Glasgow Coma Score to measure the state of consciousness of the subject. For adolescents, neurocognitive function is not measured by a neurocognitive test battery; only the Glasgow Coma Score will be assessed.
- The Glasgow Coma Score which indicates the degree of consciousness, is sum of the Eye Opening, Verbal and Motor Response scores.
- Improvement of organ dysfunction and improvement of TTP related signs and symptoms
- Determination of biomarkers of TTP including but not limited to disintegrin-like and metalloprotease with thrombospondin repeats 13 (ADAMTS13) activity levels, including baseline functional inhibitors (see also PD assessments)

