### 6.1.2 Handling of Dropouts and Missing Data

The primary, secondary and longer term endpoint analyses will be based on available data. No imputations will be made for missing data unless otherwise specified.

If a subject had a PE prior to being randomised then there will be no replacement of missing baseline values by screening values. If a subject did not have a PE prior to being randomised then missing baseline values will be replaced by screening values. Missing data post-baseline will not be estimated or imputed for any of the parameters.

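### In the ITT table, the complete remission rule counts as a success a responder who then dies without an exacerbation or is still on daily PE, and it does not classify responders who withdraw

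*SAP*

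**What the plan says.** - **Protocol 4.1.2** lists the "Number of subjects with complete remission (defined as confirmed platelet response and absence of exacerbation").
- **SAP 6.3.2** repeats it: "Number and percentage of subjects with complete remission (defined as confirmed platelet response and absence of exacerbation").
- **SAP section 3** has the same two parts. It begins "Complete remission is defined as recovery of platelets", asks for confirmation at 48 hours on platelets and LDH, and adds absence of exacerbation.
- **Exacerbation** (SAP 6.3.2; section 3 agrees) is "recurrent thrombocytopenia following a confirmed platelet response and requiring a re-initiation of daily PE treatment after" at least 1 and at most 30 days from the last daily PE.
- **SAP section 4**, in the neurocognitive bullet, has another meaning: "Remission is defined as the absence of need for PE treatment" for at least 30 days.
- **Missing data (SAP 6.1.2):** secondary analyses use available data, and "No imputations will be made for missing data unless otherwise specified". SAP 6.1.1 makes the population total the denominator of each percentage.
- **Timing (SAP 6.3.2):** the list heading places all secondary endpoints within 30 days after the end of study drug. The analysis paragraph reports complete remission one month after the first dose.

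**The concern.** Complete remission should describe a subject who responded and stayed well. The rule instead describes a subject who responded and has no exacerbation on record. The two differ for anyone in whom an exacerbation could not be recorded. In a disease for which Protocol 2.5.2 cites 10% to 30% mortality in the acute idiopathic form, a death after response can enter the table as a success.

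At stake are the published remission percentage and its exact confidence interval in each arm. The primary endpoint, its alpha and the sample size are not touched.

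**Working it through.** **1. The plan's own figures.** No rate or sample size is given for complete remission. The only design figure is 110 subjects for the primary endpoint (SAP 6.1.4). It reproduces: events = 4 × (1.960 + 0.842)² / (ln 1.786)² = 93.4, and 93.4 / 0.85 = 109.9, so 110, or 55 per arm. In this reproduction the 15% lost subjects contribute no response.

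**2. The written rule applied to subjects with a confirmed response.**

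| After response | Can an exacerbation be recorded? | Result under the rule |
|---|---|---|
| Dies, no earlier exacerbation | No | Complete remission |
| Still on daily PE | No, daily PE has not stopped | Complete remission |
| Withdraws before the 30-day window closes | Not observed | Not stated |

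The second row can occur. Protocol 4.3 says "Discontinuation of daily PE depends on normalisation of platelet count, neurological status and other clinical and laboratory parameters", so a platelet response alone need not end PE.

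**3. Is this corrected elsewhere?** The censoring scenarios in SAP 6.3.1 (Tables 1 and 2) deal with leaving the trial, missing confirmation and not being dosed, but only for platelet response. Deaths have their own table in SAP 6.3.2, with no link to remission. SAP 6.1.2 has no failure rule. Nothing changes the first two rows for the ITT table.

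**4. Timing.** If daily PE ends on day d, the exacerbation window closes on day d + 30. At one month after the first dose (about day 30) it has closed only if d is about 0. If daily PE stopped as early as the planning median response times, the window would close at day 36 on placebo (6 + 30) and day 33.4 on ALX-0081 (3.36 + 30). So at one month it is still open for most responders. The list heading is different: study drug runs for 30 days after the very last PE, so a subject who completes it has passed the window by then, apart from cases cut short by the 90-day cap.

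**5. Size.** One subject is 1/55 = 1.8 points. Starting counts are assumed, because the documents give none:

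| Reclassified as not in remission | From 45/55 (exact 95% CI) | From 40/55 (exact 95% CI) |
|---|---|---|
| 0 | 81.8% (69.1–90.9) | 72.7% (59.0–83.9) |
| 2 | 78.2% (65.0–88.2) | 69.1% (55.2–80.9) |
| 4 | 74.5% (61.0–85.3) | 65.5% (51.4–77.8) |
| 8 | 67.3% (53.3–79.3) | 58.2% (44.1–71.3) |

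The row of 8 is about 15% of 55. It borrows the plan's loss assumption as an outer illustration and is not a forecast.

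**6. Drift between arms (illustration only).** Assume exponential response with λ = ln 2/6 = 0.1155 and ln 2/3.36 = 0.2063 per day, 2 days for confirmation, and 15% loss spread evenly over 36 days.

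- Share of losses after confirmed response = [34 − (1 − e^(−34λ))/λ]/36 = 71% on placebo and 81% on ALX-0081.
- Times 15%: 10.6% and 12.1%, or 5.8 and 6.7 of 55. The difference is about 0.8 of a subject, or 1.5 points, and it counts only if withdrawals are scored as successes.
- For deaths independent of response with mean time m days, the share after confirmed response is e^(−2/m) × λ/(λ + 1/m). At m = 5, 9 and 15 it is 25%, 41% and 55% on placebo, and 34%, 52% and 66% on ALX-0081. The documents give no m, so the result depends on the assumption.

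**The case against.** **The one-month wording can be read as a status at that time, which a dead subject does not have.** That is a natural clinical reading, but neither the definition nor the analysis paragraph makes being alive a condition.

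**The per-protocol analysis already covers this.** It does so in part. SAP section 2 limits that population to subjects who satisfactorily complete the study, and section 3 extends completion to 30 days after the last dose, so deaths and withdrawals largely drop out. But they leave the denominator as well and are not counted as failures. ITT remains the primary efficacy population. Deaths, discontinuations and platelet counts at later visits are also tabulated, so a careful reader could see part of the problem.

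**A reader might infer that withdrawals are scored as remissions.** The SAP does not say so. Under available data, exacerbation status could equally be treated as missing, which with the full denominator means not in remission. The classification is open.

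**A reader might infer a bias towards ALX-0081, since faster responders have more of their losses after response.** The direction is plausible, but the documents do not establish it. The loss calculation gives about 1.5 points, and it moves losses past response although the sample size reproduction treats lost subjects as giving no response. The death calculation needs a mean time to death, and independence of death from response, that appear nowhere in the documents. The SAP also counts death within loss to follow-up, so the two illustrations cannot be added.

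**A reader might infer that section 4 overrides the rule or drives another result.** It sits in the neurocognitive bullet, and SAP 6.1.5 reduces the computerised cognitive battery to descriptive values at each time point. It is an unreconciled second meaning. It would exclude a subject still on PE whom the main rule includes.

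**Conclusion.** The point holds for the ITT analysis. By its own terms the rule gives the wrong answer for two groups of responders: those who die without an exacerbation and those still on daily PE. For withdrawals the SAP is silent. The competing wording in section 4 and the two assessment times add to the ambiguity.

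The number of subjects affected cannot be derived from the documents. What is firm is 1.8 points per subject in an arm of 55; the shifts in step 5 rest on assumed counts. Drift between arms is likely to be small. Complete remission is a secondary endpoint with no multiplicity control, and the SAP calls its p-values exploratory, so the harm is to the accuracy of a reported rate and not to the trial's main inference. It is still worth correcting, because the error is in the rule itself and the repair is cheap.

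**What to change.** In SAP sections 3 and 6.3.2:

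- State that a subject who dies before the assessment point, or is still on daily PE at that point, is not in complete remission.
- State how withdrawal or loss before that point is classified, and add a second table under the alternative classification.
- Reconcile the one-month-after-first-dose time with the list heading and with the 30-day window after the last daily PE, so that the window can be observed. Without this step, a condition of 30 days without restarting PE could not be met by most responders at one month.
- Make the meaning of remission in section 4 agree, and record the change from protocol 4.1.2 in SAP 6.1.5.

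The cost is one derived flag, one extra table and slightly lower reported remission rates. No patient care, visit schedule or sample size changes.
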